This will be a cluster randomized control trial(C-RCT) conducted in Pune and Sangli district under field practice area of two medical colleges of Bharati Vidyapeeth University for a period of two years. The overall budget for the project is Rs. 11,449,580. The aim is to assess the efficacy of community based interventions in reducing incidence of pneumonia .To achieve 80% power and assuming intra-class coefficient of variation of 0.5, the study will randomly select and enrol 16 clusters with around 4800 children into intervention and comparison arm. The community based interventions in the form of behavioural change communication (BCC) activities under following domain will be implemented viz. child feeding practices, immunization, indoor air pollution, hand hygiene of mother at 4 occasions(after defecation, after cleaning child's bottom, before food preparation, before feeding the child), knowledge attitude and practices of mother about pneumonia, cough etiquettes. These interventions will be implemented by the project appointed field supervisors in the interventional clusters for mothers of under five children. These supervisors will be trained through project. Pneumonia surveillance will be conducted at fortnightly visits by ASHA/Anganwadi worker in both the arm for a period of one year. Incidence of pneumonia will be compared in both the arms. Quality will be assured by continuous monitoring of activities through sub-investigators. The progress of project will be reviewed in monthly meetings with partners. Assessment of efficacy of community based interventions in reduction of incidence pneumonia will done.

Protocol

1. Title of the research proposal project:

Pneumonia Research Initiative in Rural Areas and Urban Slums of Maharashtra

2. Problem statement:

Recent statistics indicates that in Maharashtra the fortnight period prevalence of ARI among children under 5 years of age is 8.5 % and 9.3% in urban and rural areas respectively (DLHS-4). Some children develop pneumonia which is responsible for 14% of total under five deaths (UNICEF 2012). Pneumonia is a leading cause of death among children under 5 years of age. One of the reasons for not achieving the Millennium Development Goal 4 (reduction in child mortality) is poor access to health facilities and paucity of trained human resources in primary health setups.

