- 2. Proforma for collection of information from study subjects(baseline survey)
- 3. Behavioural Change Communication(BCC) material
- 4. Booklet for mother
- 5. Fortnightly Pneumonia surveillance tool (Diary).

Operational Definition of Community Based Interventions (CBI): These are Behavioural Change Communication (BCC) activities conducted by ASHA/Anganwadi worker (AWW) for mothers of under five children with respect to following domains:

- 1. Child feeding practices which include exclusive breast feeding and appropriate weaning.
- 2. Immunization of under five children.
- 3. Indoor air pollution (reduction in use of biomass fuel and smoking).
- 4. Hand hygiene of mother/care taker of child: Correct hand washing steps at following 4 occasions: After defecation, after cleaning child's bottom, before food preparation, before feeding the child.
- 5. Knowledge Attitude and Practices of mother about pneumonia: Signs and symptoms of pneumonia, danger signal of severe disease and appropriate care seeking.
- 6. Cough etiquettes.

The BCC activities will include interpersonal communication, group discussions and demonstration etc. Outcome of these Community based interventions will be measured in children i.e. incidence and also deaths due to pneumonia.

Study duration: Two years.

Methodology:

The study will be conducted in phase wise manner. The activities in different phases are listed below:

Phase 1: Preparation (2 months)

- 1. Development and validation of research tools: Tools as described above will be developed and used for data collection. These tools will be quantifiable and objective. The team of investigators including paediatrician, biostatistician and anthropologist/social scientist will be involved in development and drafting of study tools. While preparing the tools available training booklets will be extensively used. All the tools will be bilingual and will be piloted for validity, question framing, relevance, sequencing and time required for filling the tools. The tools then will be finalized after making necessary modifications.
- 2. Appointment of Field supervisor (FS) and training. Training of FS
- 3. Baseline data in brief and with limited objectives will be collected from all clusters prior to randomizing them into intervention and control clusters.

Objectives of baseline survey:

- a. To obtain basic socio-demographic information of the family (age, sex, income, education & occupation)

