Phase 2: Baseline/Enrolment (3 months): Enlisting of study subjects in intervention and comparison clusters. This will be done through house to house visits by ASHA/AWW in their respective cluster. Written informed Consent will be taken from mother by ASHA/AWW In first visit following details will be obtained after informed consent.

- a. Basic socio demographic information(will be collected prior to randomising them into intervention and control cluster)
- b. Enlisting all mothers of under five children and expectant mothers.
- c. Enlisting all under five children
- d. Selection and random allocation of the clusters to intervention and comparison arm

All the data collected will be entered in predesigned excel sheet and database will be generated for further analysis.

Phase 3: Intensive Community based Intervention (4 months)

1. First round of BCC activities for mothers: This will be conducted by the trained and equipped Field supervisor in small groups consisting of about 10 mothers. Every week she will conduct one session for about 10 mothers in anganwadi /community hall in intervention clusters only. Some of these sessions will be attended by investigators. All mothers in her cluster will be educated in two months.

The content of BCC activities will be

- Child feeding practices which include exclusive breast feeding and its distinctive advantages and appropriate weaning.
- Role of Immunization of under five children in preventing various vaccine preventable diseases.
- Hazards of biomass fuel and use of substitutes like smokeless chulla, LPG etc.
- Hand hygiene of mother/care taker of child: Correct hand washing steps at following 4 occasions: After defecation, after cleaning child's bottom, before food preparation, before feeding the child.
- Knowledge, Attitude and Practices of mother about pneumonia: Signs and symptoms
 of pneumonia, danger signal of severe disease and appropriate care seeking, timely
 contact by mother or care taker to the ASHA/AWW etc.

BCC material in local language developed especially for mothers will be handed over to them. This material will help mothers to adopt practices which will minimize risk factors of pneumonia. Subsequently enrolled subjects (delivered women, newborns, including migrated) will also be receive BCC activities in a special session.

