2. Second round of BCC activities: This will be conducted for reinforcement of the information delivered in first round. It will be conducted again in small groups after 2 months of first round and completed in two months. In this round emphasis will be given on skills acquired and demonstration by participants.

Various BCC activities will be supervised by sub-investigators.

Training of ASHA/AWW:

Investigators will train AWW & ASHA from intervention arm to orient them about the objectives, importance of project and their role in the project for surveillance.

Contents of the training modules:

- a. Introductory contents pertaining to pneumonia: protocol specific training, IMNCI guidelines for ARI/Pneumonia, diagnosis and standard management of pneumonia, problem statement of ARI/Pneumonia in their area.
- b. Surveillance related training: Fortnightly surveillance, maintenance of diary
- c. Communication skills and conducting session for mothers.
 Investigators will train all AWW and ASHA from both the arms regarding surveillance. Duration of training for ASHA/AWW:One day.

ASHA/AWW/FS from intervention arm will be requested to share their mobile numbers with mothers so that in case of any need like of sickness of child mother can contact them. The importance of response to mothers call will be emphasized as it may ensure appropriate management of child's illness and prevent the mortality. Training about fortnightly surveillance will be imparted to them.

Information about available emergency services like help line 108,102 will be given and ASHA/AWW/FS will communicate their mobile numbers to mothers/expectant mothers and will appeal to contact on same whenever the child is sick.

Phase 4: Followup and continued Intervention (12 months)

Pneumonia surveillance: This will be done in intervention arm for a period of one year by AWW/ASHA in rural area and AWW in urban slums through fortnightly house to house visit and enquiring about signs and symptoms related to pneumonia in preceding fortnight. This will help to calculate the fortnight incidence of pneumonia. Fortnightly visits will be adequate to get incidence of pneumonia in addition to this the mobile numbers of ASHA will be shared to mothers so that in case of any need like sickness of child mother can contact them. This will help to record attacks of pneumonia if any between the two fortnight visits.

Following definitions from IMNCI Guidelines will be used:

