Pneumonia: child with cough or difficulty in breathing as having pneumonia.

severe pneumonia: If the symptoms are associated with lower chest wall in drawing or subcostal retraction,

Very severe pneumonia: If there is a danger sign such as central cyanosis, or severe respiratory distress, convulsion, inability to rouse the child or if the child is unable to drink.

Interval: An episode of pneumonia after 7 days of previous episode will be counted as a new episode.

If answer is yes then ASHA/AWW will enter the information in the diary maintained by her and submit information to site investigators(SI). They will confirm the pneumonia using WHO IMNCI protocol.

Appropriate management of child's illness will be ensured. This record will be submitted in fortnightly meeting (one will coincide with their monthly meeting) with FS and the same will be updated periodically. In addition, information about any death among under five children will be collected and the cause of death will be ascertained.

Continued intervention: Will be given by field supervisor (FS) through monthly house to house visits During her house to house visits in intervention arm FS will interact with all mothers and enquire about practicing the methods, skills steps learnt during intensive intervention. In case of unsatisfactory response FS will reinforce the knowledge and skills.

The sub investigator will supervise a pair of cluster from intervention and comparison arm and will do surprise home visit to cross check information collected by AWW/ASHA.

In comparison clusters ASHA/AWW will continue their role as per existing guidelines and collect information about pneumonia and deaths due to pneumonia through fortnightly house to house visits and submitted to FS fortnightly. And AWW and ASHA will continue to

promote all activities that are part of national programme (immunisation, optimal feeding practices) in control sites.

Midterm evaluation of the project will be done by third party at the end of three months of surveillance.

Detection and referral of pneumonia cases is a part of routine activity of ASHA/AWW workers so stopping of these duties is not advisable. And they will be closely monitored by field supervisors and sub investigators.

Standard care for ARI / Pneumonia will be provided to referred children through our own institutions and partner in public sector in two districts.

Phase 5: Data Analysis (2 months) and Final Report writing (1 month)

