1. Information about Incidence of pneumonia will be generated and findings will be compared to determine the change in intervention and control clusters. Separate analysis for overall change in childhood mortality and morbidity will be done.

Report will be shared with all stakeholders for review, discussion and comments. Final report will be prepared by incorporating comments. The final report will be shared in the closure meeting and then submitted to the funding agency.

Continuous monitoring: Will be done through on job supervision and monthly review meetings with all the stakeholders.

Process indicators:

- 1. Evaluation of competencies learned by ASHA through training
- 2. Percentage of mothers trained in first round of BCC activities.
- 3. Percentage of mothers trained in second round of BCC activities.
- 4. Percentage of children diagnosed with pneumonia (fortnightly)
- 5. Number of cases cross checked by the field supervisor per month
- 6. Number of cases cross checked by the sub-investigator per month.

Key Outcomes:

Primary Outcome-Incidence of pneumonia in both the arms will be calculated and compared. Secondary Outcome-Morbidity rates including diarrhea in both the arms.

Data Management: Procedures involving design of data collection forms, data entry system and data quality management will be outsourced to a reputed statistical firm which has senior statistician with PhD with more than 15 years of experience of handling various international projects.

Data collection and entry: Each study subject will have a unique serial number which will be mentioned on every tool. Validity checks for the data will be applied and outliers will be confirmed.

Plan of data analysis: Data will be analyzed and summarised as proportions, percentages, mean and standard deviation. Data will be analyzed using STRATA (version 6.0).

Data Preservation:

All hard copies of the study tools and other study documents will be archived for at least five years after submission of final report in the department of Community Medicine, BVU Medical College, Pune. Soft copies will be stored in DVDs and external hard disc for minimum seven years. The data if requested may be shared for the purpose of research in future at other sites with due acknowledgement.

Timeline of the research:

Activity											N	lor	nth	S										
	_	7	3	4	2	9	7	8	6	10	11	12	13	14	15	16	17	18	19	50	21	22	23	24
Phase 1: Preparation										•	`	`	•	•	`	`	•	`	•					

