- 7. Interventions incorporated in this study will have enormous collateral benefits in the form of reduction in morbidity and mortality due to major infectious diseases specially diarrhea and vaccine preventable diseases. As well as positive behavioral change in mothers will lead to similar effect on siblings.

Patents: None

Quality assurance in the project:

Following measures will be incorporated into the study implementation design at several levels:

Meeting of all partners and investigators will be conducted for assuring high standard of quality of the study. Periodical meetings will be conducted to discuss interpretation of the statistics generated and to review the progress of the study at all sites.

Quality checks will be applied at data collection and entry level. File supervisor will randomly cross check 5% of the study tool for completeness and appropriate coding of the answers and sub-investigator will cross check 2% of the forms through surprise visits. Necessary actions will be taken at appropriate level.

Ethics and Research Governance:

The study will be started after obtaining approval from the Institutional Ethics Committee (Registration No. ECR/313/Inst/MH/2013) which is approved by competent authority and Health Ministry Screening Committee (HMSC). Confidentiality of all the study participants will be maintained. It will be ensured that personal identity of any of the participant will not be revealed.

Public Engagement:

The host organization being an academic training institute health awareness programmes are routinely conducted in the field practice areas of urban and rural health centres. In the initial stage of the project, investigators will personally orient community leaders about the

intentions of the research project. They will be requested to appeal the community for active participation in the study. The initiation and findings of the project will be shared with the community through routine community oriented/based activities.

Dissemination of the Findings:

We desire to disseminate the study results in various international and national scientific journals and also present in various scientific platforms. The study findings will be shared with policy makers in government sector through investigators and partners.

6. Risk mitigation: Minimum risk is predicted in this project.

- Attritions specially amongst field supervisors: This will be addressed by training and subsequent appointment of wait listed candidates.

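### The operational definition has the ASHA/AWW, who record the primary outcome, deliver the intervention, while the summary and Phases 3 and 4 give delivery to field supervisors; the text should be reconciled so that recorders do not deliver.

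*Protocol*

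**What the plan says.** On who delivers the behaviour change communication (BCC), the Protocol gives two answers.

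- Operational Definition of Community Based Interventions: "These are Behavioural Change Communication (BCC) activities conducted by ASHA/Anganwadi worker (AWW) for mothers of under five children".
- Opening summary: "These interventions will be implemented by the project appointed field supervisors in the interventional clusters for mothers of under five children".
- Phase 3, first round of BCC: "This will be conducted by the trained and equipped Field supervisor in small groups consisting of about 10 mothers".
- Phase 4, continued intervention: "Will be given by field supervisor (FS) through monthly house to house visits".

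The section on training of ASHA/AWW points both ways. It first describes the orientation of intervention-arm workers as covering the project's aims and "their role in the project for surveillance". Item c of the training contents is then "Communication skills and conducting session for mothers". A later sentence says that workers in both arms are trained on surveillance.

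On the outcome, the summary and Phase 4 have ASHA/AWW visit homes fortnightly in both arms, ask about symptoms in the preceding fortnight and enter positive answers in a diary. Site investigators then confirm the case by the IMNCI protocol. Diary records go to the field supervisor every fortnight in both arms. The process indicators include "Number of cases cross checked by the field supervisor per month". Quality assurance adds: "File supervisor will randomly cross check 5% of the study tool for completeness" (apparently the field supervisor), the sentence going on to coding of answers, and a 2% check by sub-investigators through surprise visits.

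**The concern.** The operational definition is where a reader looks to learn what is being tested and by whom it is given. If a site follows it, the worker who delivers BCC to a mother also asks her every fortnight whether the child has had cough or difficult breathing, and decides whether a case enters the diary. Project BCC is given in intervention clusters only, so this double role would exist in one arm only.

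No masking is described, and none is practicable for the worker or the mother in a BCC trial. The outcome starts from reported symptoms, so it depends on who asks and how. A difference between arms in the chance that a true episode is recorded passes straight into the primary comparison, and no later analysis can separate it from an effect of BCC.

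**Working it through.** There is no stated figure to reproduce; the check is a comparison of the text.

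**1. Who delivers?**

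| Place in the Protocol | Deliverer |
|---|---|
| Opening summary | Field supervisor |
| Operational definition | ASHA/AWW |
| Phase 1, field supervisor training | Field supervisor (competence assessed by demonstrating a BCC session) |
| Phase 3, first round | Field supervisor |
| Training of ASHA/AWW, opening sentence | ASHA/AWW role is surveillance |
| Training of ASHA/AWW, item c | ASHA/AWW trained to hold sessions |
| Phase 4, continued intervention | Field supervisor |

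The definition and item c stand against the rest. The weight of the text favours the field supervisor, but the definition is the formal statement.

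**2. Who controls entry of the outcome?** ASHA/AWW, in both arms. Every later step (submission, confirmation, cross-check of cases) starts from what they entered.

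**3. What follows under each reading?**

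- *ASHA/AWW deliver.* Deliverer and first recorder are the same person in intervention clusters. In comparison clusters the recorder does her routine work, including promotion under the national programme, but gives no project BCC.
- *Field supervisor delivers.* The first recorder is not the deliverer. The deliverer still receives the diaries, monitors the recorders and cross-checks cases. This is a lesser overlap, and the Protocol does not say which supervisor checks which cluster.

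**4. What do the safeguards catch?**

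- *Site-investigator confirmation* begins only after a positive entry. It can remove false positives. It cannot find an episode that was never entered.
- *The 5% check* concerns completeness and coding of forms. It is not designed to verify whether episodes were missed, whoever performs it.
- *The 2% check by surprise visit* could find missed episodes, but it is small. It is not described as masked, and each sub-investigator supervises one cluster from each arm and so would know the allocation.

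**5. Direction.** Write d_I and d_C for the probabilities that a true episode is recorded in the intervention and comparison arms. Then

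observed rate ratio = true rate ratio × (d_I / d_C).

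The Protocol gives neither probability. The values below are assumptions, chosen only to show that the sign is open:

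- No true effect, d_C = 0.90, d_I = 0.80: 1.00 × 0.80/0.90 = 0.89, a spurious benefit.
- True ratio 0.50 (the hypothesised halving), d_C = 0.80, d_I = 0.90: 0.50 × 0.90/0.80 = 0.56, a real benefit understated.
- To create the whole hypothesised halving from no effect, d_I / d_C would have to be 0.50, for example 0.45/0.90.

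The first case could arise if a deliverer under-records. The second could arise because intervention mothers are taught the signs of pneumonia and timely contact, and because intervention-arm staff are asked to share their mobile numbers with them.

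**The case against.** The strongest reply is that this is one unreconciled clause and one training item. The summary, the field supervisor training, Phase 3 and Phase 4 agree on the field supervisor, and content, format and rounds of BCC are laid out. Using ASHA/AWW for detection is also reasoned: the Protocol notes that detection and referral are routine duties which it would be inadvisable to stop. Recording, submission to the supervisor and monitoring take place in both arms, and site investigators confirm cases. All of that stands. It makes the matter easy to repair; it does not make the definition harmless to a site that follows it.

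A reader might go further than the text allows in four ways.

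- *That the plan will produce false efficacy.* The direction is not determined, as shown above. Only a risk of bias can be claimed.
- *That supervisors verify the outcome in the clusters where they deliver.* Phase 3 ties a supervisor to a cluster for BCC sessions, but no section allocates the case cross-checks to clusters.
- *That the 2% check is the only independent safeguard.* This overlooks confirmation by site investigators, who are not named as deliverers of BCC.
- *That a percentage bias can be quoted.* Any such figure only restates the assumed under-recording.

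**Conclusion.** The concern holds in a limited form. The Protocol contradicts itself on who delivers the intervention. If the operational definition is followed, the person who decides what first enters the outcome diary is also the person delivering BCC, in one arm only. The result is a risk of differential ascertainment of the primary outcome in either direction, only partly covered by the stated safeguards. Its size cannot be derived from the documents.

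The conclusion rests on two inferences: that the trial is unmasked, which follows from the nature of BCC and the absence of any masking statement; and that the definition could be followed literally, although most of the text points the other way. If field supervisors deliver, the lesser overlap through diary receipt and case cross-checks remains. Because the repair is almost free and protects the primary comparison, it should be made.

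**What to change.** 1. In the operational definition, name the project-appointed field supervisors as those who conduct BCC, in line with the summary, the Phase 3 first round and the Phase 4 continued intervention.
2. Delete item c (communication skills and holding sessions for mothers) from the ASHA/AWW training contents. Outcome recorders then do not deliver BCC, and workers in both arms receive the same surveillance training.

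The cost is Protocol wording only.

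It may be tempting also to have field supervisors exchange diary checks within the cluster pairs assigned to sub-investigators. This should not be adopted. Each pair is one intervention and one comparison cluster, so the exchange would send the unmasked deliverer to check comparison diaries. It would bring BCC staff into clusters that the plan tries to protect from contamination by geographical separation, and it presumes supervisor numbers that the Protocol does not give.

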Aim: To assess the efficacy of community based interventions in reducing incidence of pneumonia.

Objectives:

To compare the incidence of pneumonia among under five year children from intervention and comparison clusters after selected community based interventions.

[figure not shown]
5. Study Protocol/Detailed research plan:

Study design: A cluster randomized trial in Pune and Sangli district stratified by urban slums and villages.

Study area: Bharati Vidyapeeth University is a multidisciplinary and multi centric university having two medical colleges in Pune and Sangli districts of Maharashtra state of India. This study will be carried out in 4 sites under the urban and rural field practice area of these two medical colleges. Each site is having 9-16 clusters of slums/ villages.

Number of clusters and sample size calculation:

Figure-1

A review article indicates that incidence of childhood pneumonia is 0.2 to 0.5 per child per year (Ghimire M. et al 2012). This is equivalent to 20% to 50% of incidence of pneumonia. For sample size calculations we have assumed the incidence rate at 30%. Community based intervention is expected to reduce the incidence rate by 50%. The curve required for various powers and number of clusters is shown in figure-1. Sample size assumptions and estimations are reviewed by a statistician.

To achieve 80% power and assuming intra-class coefficient of variation to be 0.5, the study will need to enrol minimum 15 clusters of average 300 size. However we have decided to include 16 clusters.

Thus the total number of children under 5 years to be enrolled in the study will be about 4800.

The field practice areas of both medical colleges together have 47 available clusters; 16 clusters will be selected randomly and allocated to intervention arm and comparison arm by randomization. Thus there will be 8 clusters in intervention arm and equal number in comparison arm.

All under five year children residing in the selected clusters and their mothers (including expectant mothers) will constitute study subjects. The process of inclusion of subjects (mothers and children) will continue throughout the study period. Those children who complete five years of age in the project period will be excluded. However, these children will be considered while calculating denominator of children-months.

Study tools: Following tools will be developed and used for data collection and intervention

- 1. Trainer's modules

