- b. To determine proportion of women in reproductive age group

- c. To determine incidence of pneumonia in last one year and incidence of ARI in last one month and also to measure child mortality in last one year including mortality due to pneumonia.
- d. To determine sources contributing to indoor air pollution like type of fuel used for cooking, smoking by family member, overcrowding.
- e. To measure proportion of other risk factors like low birth weight, birth order, malnutrition, breast feeding, immunization status of under five year old and KAP of mother about pneumonia including care seeking behavior.
- 4. Intervention cluster will be geographically separated so as to reduce contamination. There are minimal chances of contamination however some may occur during nonformal communication of ASHA AWW with each other.
- 5. Identification and orientation of private medical practitioners, concerned Taluka Health Officer, Medical Officers, Auxiliary Nurse Midwives (ANM).
- 6. Accredited Social Health Activist (ASHA), Anganwadi workers (AWW) from the selected clusters will be identified and they will be incentivized through the project.

Field supervisors will be trained regarding

- a. Introductory contents pertaining to pneumonia: protocol specific training, IMNCI guidelines for ARI/Pneumonia, diagnosis and standard management of pneumonia, problem statement of ARI/Pneumonia in their area.
- b. Intervention related training: Relevance of selected risk factors in reduction of pneumonia. Methods to reduce the same through Behavioural Change Communication activities.
- c. Surveillance related supervisory training:
- d. Communication skills and conducting session for mothers above mentioned areas. Over and above their role as a supervisor will be explained and taught to them.
- e. Initial Training: Two days and one additional day for hands on training in the field. The material intended to be used by them for Behavioural change communication (BCC) during interpersonal communication with mothers will be shared with them and their competency will be assessed in the field through demonstration of conducting a BCC session for mothers.

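### The pre-randomisation survey of pneumonia and ARI is not used to balance the 16 clusters; constraining the draw on it, within the slum/village strata, would be a cheap gain in balance and precision

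*Protocol*

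**What the plan says.** - **Timing of the survey.** Phase 1: Preparation, item 3: "Baseline data in brief and with limited objectives will be collected from all clusters prior to randomizing them into intervention and control clusters".
- **Content of the survey.** Objective c of the baseline survey: "To determine incidence of pneumonia in last one year and incidence of ARI in last one month". Objectives d and e add fuel, smoking, overcrowding, malnutrition and other risk factors.
- **Phase 2, item a, is narrower.** There the item marked as preceding randomisation is only this: "Basic socio demographic information(will be collected prior to randomising them into intervention and control cluster").
- **Design.** Study design: "A cluster randomized trial in Pune and Sangli district stratified by urban slums and villages".
- **Allocation.** Number of clusters and sample size calculation: "16 clusters will be selected randomly and allocated to intervention arm and comparison arm by randomization". It continues: "Thus there will be 8 clusters in intervention arm and equal number in comparison arm". Phase 2, item d, adds only that selection and allocation are random. Neither place says how the strata enter the draw.
- **Geography.** Phase 1, item 4, asks for intervention clusters to be kept apart geographically to limit contamination.
- **Variation assumed.** "To achieve 80% power and assuming intra-class coefficient of variation to be 0.5, the study will need to enrol minimum 15 clusters of average 300" children.

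No section uses the baseline pneumonia or ARI rates in the allocation.

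**The concern.** The primary comparison rests on 8 clusters against 8. On the protocol's own assumption, clusters differ widely in underlying pneumonia rate, and that variation, not the number of children, dominates the error of the comparison. The protocol plans to collect a measure related to the outcome in every cluster before the draw and then does not use it to steer the draw. Clusters within one stratum still differ, so stratifying by slum and village does not settle the matter.

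Allocation happens once. An analysis plan written later can adjust for imbalance but cannot undo a poorly balanced draw, so this belongs in the protocol. At stake are the precision of the estimate and how credible it looks if the arms start out visibly different.

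**Working it through.** **Inputs from the protocol.** Clusters per arm c = 8; 300 children per cluster; one year of surveillance; control rate 0.30 per child-year; halving expected; k = 0.5. The protocol calls this last figure an intra-class coefficient of variation; it is read here as the between-cluster coefficient of variation.

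**Assumed, because not stated.** Two-sided 5% test; no dropout; share g of between-cluster variance explained by the strata (0, 30%, 50%); correlation r between baseline and follow-up cluster rates (0.3, 0.5, 0.7).

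**The plan's own figure.** The protocol gives no figure for chance imbalance. Its nearest figure is the minimum of 15 clusters. The usual unmatched formula at k = 0.5, two-sided, gives 10.2 to 11.3 clusters per arm (about 20 to 23 in total), so 15 is not reproduced. Alpha is not stated and Figure-1 is not shown. That is a separate matter; it is noted because the trial has little precision to spare.

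**Step 1: spread of the ratio under no effect.**
- Rate scale: k × sqrt(2/c) = 0.5 × sqrt(2/8) = 0.25. With Poisson noise, 1/(0.30 × 300) = 1/90 per cluster: sqrt((0.25 + 0.0111) × 2/8) = 0.255.
- Log scale, log-normal cluster rates: variance ln(1 + 0.5²) = ln 1.25 = 0.223, so sqrt((0.223 + 0.011) × 2/8) = 0.242.

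**Step 2: how often the ratio falls beyond 0.75 or 1.33.** On the log scale the limit is ln(1.333) = 0.288, and 0.288/0.242 = 1.19, a two-sided tail of about 23%. Simulation gives about 24%. The rate-scale value 0.255 gives about 26%.

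**Step 3: allowing for the strata.** If they explain 30% of the between-cluster variance: sqrt((0.7 × 0.223 + 0.011) × 2/8) = 0.204, a tail of about 16% (simulation about 17%). If 50%: sqrt((0.5 × 0.223 + 0.011) × 2/8) = 0.175, about 10% (simulation 10-11%).

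**Step 4: validity.** In 100,000 simulated null trials with unstratified allocation, the cluster-level t-test rejected in 4.5% to 4.6%. Type I error is not inflated.

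**Step 5: what constraining the draw buys.** There are C(16,8) = 12,870 unrestricted splits. In the simulation the best-balanced 10% on baseline rate were kept and one was drawn. If balance were perfect, the spread would shrink by sqrt(1 − r²): 0.242 becomes 0.231, 0.210 and 0.173, with tails of about 21%, 17% and 10%. Simulation with the 10% rule and no strata effect comes close:

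| r | Beyond 0.75/1.33, unconstrained | Constrained |
|---|---|---|
| 0.3 | 24% | 21-23% |
| 0.5 | 24% | 18% |
| 0.7 | 24% | 11% |

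**Step 6: power for a halving, log scale, no strata effect.**

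| r | Neither | Covariate only | Constraint and covariate |
|---|---|---|---|
| 0.3 | 74% | 75% | 75% |
| 0.5 | 74% | 82% | 84% |
| 0.7 | 74% | 92% | 94% |

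The constraint adds about 2 points at most once the covariate is in the model. The 74% is on the log scale; on the rate-difference scale the same inputs give 69% (normal) or 63% (t, 14 df).

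The simulation balanced one variable. Balancing three at once would hold each of them less tightly.

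**The case against.** The strongest reply is that nothing stated is wrong. The design is a valid randomisation, it is declared stratified, and chance imbalance is exactly what a cluster-level test allows for. This stands, and it rules out several stronger readings:

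- **That allocation is a plain random split.** The Study design line declares slum/village strata. What is missing is only how they enter the draw. The 24% is therefore the value for strata that explain nothing, and an upper value otherwise.
- **That a chance 25% difference would pass as an effect.** At k = 0.5 it is about one standard error of the null difference, and the test still rejects in about 5% of null trials.
- **That the baseline rates are known at the draw.** They are planned, by recall over a year and a month, and Phase 2, item a, marks only socio-demographic data as preceding randomisation.
- **That the allocation method costs some 20 points of power.** Nearly all of the gain at r = 0.5 and 0.7 comes from the covariate. That is an analysis choice which an unseen analysis plan may already contain.

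It is also fair that r is given nowhere. Recall by mothers may track prospective, investigator-confirmed surveillance poorly, and at r = 0.3 the gain is slight.

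What remains is that the outcome-related baseline is planned before a one-time draw and left unused. Recall error gathered before allocation cannot depend on the assigned arm, so even an imperfect baseline can be used for balancing.

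**Conclusion.** The point holds as a cheap improvement, not as an error. Allocation is restricted at most by the slum/village strata, in a way that the text does not specify, and the baseline pneumonia and ARI rates are not used. With 8 clusters per arm and k = 0.5, the null standard deviation of the log rate ratio is about 0.24 to 0.25. About 24% of allocations give a ratio beyond 0.75/1.33, or about 17% if strata explain an assumed 30% of the variance.

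The loss is in precision and credibility. A reader might infer bias or an inflated false-positive rate; the calculations support neither. The size depends on reading 0.5 as a coefficient of variation: at an assumed k of 0.25, fewer than 2% of null trials show an apparent benefit of 25% or more. The gain depends on the unknown r. The constraint mainly improves balance, and the baseline covariate supplies most of the power.

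**What to change.** 1. Reconcile Phase 2, item a, with Phase 1, item 3, and the baseline objectives, so that the pneumonia and ARI baseline is clearly complete and locked before allocation.
2. In Number of clusters and sample size calculation and in Phase 2, item d, state how the strata enter the draw, and that allocation is 8:8 by constrained randomisation within them. List the splits compatible with the geographical separation in Phase 1, item 4. Keep the best-balanced share (for example 10%) on baseline pneumonia rate, ARI rate and number of under-fives, and draw one at random. As an illustration, two strata of 8 clusters, each split 4:4, give 70 × 70 = 4,900 splits before the separation rule and 490 at 10%. Check that enough splits remain once that rule is applied.
3. Analyse at cluster level with stratum and baseline rate as covariates, or by a permutation test over the retained splits. An unadjusted test after constraining is conservative and would waste much of the gain.

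**Cost.** Protocol wording and a short program run once, with no extra fieldwork. One degree of freedom goes to the baseline covariate, and the analysis must respect the constraint. If recall proves uninformative, the gain is close to zero.
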